## **12.5. Clinical Laboratory Evaluations**

Summaries of clinical laboratory data will be provided for subjects in the Safety Population based on central lab data. No inferential statistics will be provided. All laboratory assessments collected after date of first dose of study drug and up to +30 days after the last dose will be included in the summary tables. All laboratory data will be listed.

### **12.5.1. Summaries of Numeric Laboratory Results**

Quantitative values and change from baseline in quantitative values will be summarized by planned nominal time and treatment for each quantitative lab. Listings of all laboratory results and reference ranges will be provided. Laboratory values that fall outside the reference range will be flagged.

### **12.5.2. Graded Abnormalities**

Clinical laboratory results will be graded according to criteria specified in the protocol using DMID Adult Toxicity Table (2007), if applicable.

Any graded abnormality that occurs following the initiation of study drug and up to +30 days after the last dose, and represents at least 1-grade increase from the baseline assessment is defined as treatment emergent. The number and percentage of subjects experiencing treatment-emergent graded toxicities will be summarized by treatment group. A laboratory shift table will be provided to show the baseline grade to the maximum post baseline grade. Laboratory values that do not meet the graded laboratory abnormalities are assigned grade 0 in the shift table.

## **12.6. Vital Signs**

Vital sign data (blood pressure [BP], heart rate [HR], and body weight) will be summarized by treatment, visit, and planned time and will be listed by subject, visit, treatment, planned time and actual date and time. Change from baseline for BP, HR, and body weight will also be summarized.

## **12.7. Electrocardiograms**

The ECG data and change from baseline values will be listed and summarized by treatment, visit and planned time. The number and proportion of subjects with QTcF >450, >480 or >500 msec; or changes of >30 -≤60 msec, or >60 msec will be summarized by treatment over time.

Clinically significant abnormal ECG findings will also be summarized.

## **12.8. Pulmonary Diffusion**

Pulmonary diffusion data, including actual and percent change from baseline values will be listed and summarized by treatment and visit.

## **12.9. Pregnancy**

If any female subjects or female partners of male subjects become pregnant during the study, a listing will be provided.

## **12.10. Other Safety data**

Number and percentage of attacks that required additional medical care and type of medical care will be summarized by treatment group, if data warrant.

### 13. PHARMACOKINETIC ANALYSES

#### 13.1. Drug Concentration Measures

Plasma concentrations of BCX7353 will be measured by a validated assay. These plasma concentrations will be listed for all subjects with a result (including those from placebo-treated subjects) and summarized by active treatment and time using the Safety Population. Linear and semi-log figures for individual subjects as well as mean and median concentration-time data will be generated.

#### 13.2. Deriving and Summarizing Pharmacokinetic Parameters

Steady-state BCX7353 (metabolites if measured) plasma PK parameters will be estimated over the sampling interval for each subject using noncompartmental analysis (Phoenix WinNonlin version 6.4 or later, Certara, LP). Steady-state BCX7353 PK parameters collected on Day 14 or Day 28 will be combined by treatment group for summary statistics. The PK population will be used for the evaluation of PK parameter data.

The PK parameters that may be estimated are listed below. Additional analyses may be conducted as appropriate.

Pharmacokinetic Parameter	Definition
$AUC_{\tau}$	Area under the plasma concentration versus time curve over the dosing interval ( $\tau$ ) (ie, 8 hours for q8h dosing)
$C_{av,ss}$	Average steady-state plasma drug concentration during multiple-dose administration
$C_{max}$	Maximum observed concentration of drug
$C_{\tau}$	Observed drug concentration at the end of the dosing interval ( $\tau$ )
$t_{1/2}$	Estimate of the terminal elimination half-life of the drug, calculated as $0.693/\lambda_z$
CL/F	Apparent oral clearance after administration of the drug calculated as $Dose/AUC_{\tau}$
$\lambda_z$	Terminal elimination rate constant, estimate by linear regression of the terminal elimination phase of the natural logarithm of concentration of drug versus time curve
$V_z/F$	Apparent volume of distribution of the drug
$T_{max}$	Time of $C_{max}$

For the calculation of individual PK parameters, all PK concentrations that are BQL will be set to zero except when an individual BQL value falls immediately between two quantifiable values, in which case it will be set to missing. Actual elapsed time from dosing will be used to estimate

all the individual plasma PK parameters.

The appropriateness of estimation of  $\lambda_z$  and  $\lambda_z$ -derived parameter estimates will depend on an accurate estimation of the terminal elimination phase of the analyte, based upon inspection of individual subject PK profiles.  $\lambda_z$  and  $\lambda_z$ -derived parameter estimates that are considered by the Clinical Pharmacologist at BioCryst to be unreliable may be excluded from the summary statistics. In general, a minimum of three time points in the terminal phase with unadjusted  $R^2 \geq 0.7$  will be required to report  $\lambda_z$ .

Plasma PK parameters, except  $T_{max}$ , will also be summarized based on log transformed data.

Dose proportionality will be analyzed using a power model, and the slope and its 90% confidence interval will be estimated. A secondary assessment of dose proportionality will be made using log transformed dose normalized AUC and  $C_{max}$ , which will be analyzed by using an analysis of variance including terms for dose effects. Each dose will be compared with the 125mg dose on a pair-wise basis, with the ratio and its 90% confidence interval estimated.

The trough plasma BCX7353 concentrations obtained pre-dose or 24 hour post-dose on Days 14, 15, 28 and 29 (as applicable) will be plotted and summarized by treatment group. Achievement of steady-state will be assessed by calculating the 90% CI of the slope of the linear regression of Days 14-29 trough concentration versus Day for each treatment group.

The number and proportion of subjects with average plasma BCX7353 trough concentrations ( $C_{tau}$ ) above 4x and 8x kallikrein inhibition  $EC_{50}$  values (35.8 ng/mL and 71.6 ng/mL) will be summarized by treatment group.

For each subject, the percent of plasma BCX7353 trough concentrations ( $C_{tau}$ ) above 4x and 8x kallikrein inhibition  $EC_{50}$  will be derived and summarized by treatment group.

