**Table 7: Pharmacokinetic Parameters**

Pharmacokinetic Parameter	Definition
$AUC_{\tau}$	Area under the plasma concentration versus time curve over the dosing interval ( $\tau$ ) (i.e., 24 hours for once daily dosing)
$C_0$	Observed concentration predose
$C_{av,ss}$	Average steady-state plasma drug concentration during multiple-dose administration
$C_{max}$	Maximum observed concentration of drug
$C_{\tau}$ (steady state only)	Observed drug concentration at the end of the dosing interval ( $\tau$ )
CL/F	Apparent oral clearance after administration of the drug calculated as $Dose/AUC_{\tau}$
$\lambda_z$	Terminal elimination rate constant, estimate by log linear regression of the terminal elimination phase of the concentration of drug versus time curve
$V_z/F$	Apparent volume of distribution of the drug
$t_{1/2}$	Estimate of the terminal elimination half-life of the drug
$T_{max}$	Time of $C_{max}$

In all derivations of PK parameters, zero will be substituted for concentrations below the quantification limit (BQL) of the assay. Samples which are BQL, but are between 2 samples with detectable concentrations will be excluded from PK analysis.

Dose proportionality will be analyzed using a power model and an ANOVA model based on dose normalized PK parameters. Additional analyses may be conducted as appropriate.

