- n Subjects will be randomized by the Sponsor on or after the screening visit and is contingent upon review of screening visit data entered into the eCRF subsequent questions the Sponsor may have. Randomization will trigger shipment of a kit of study drug for the first 14 days and an automatic resupply to arrive on-site at approximately study Day 10 after entry into the eCRF system that the subject has had a Day 1 visit. More details on randomization and kit shipment will be provided to the site.
- o The Investigator (or designee) will provide a diary for collection of HAE attacks (screening through follow-up) and study drug dosing (Days 1-28) at screening, Day 1, Day 14 and Day 29. Diaries will be collected on Day 1 (screening diary), Day 14, Day 29 and follow-up. At each visit and phone call, the Investigator (or designee) will review proper recording of attacks and dosing (as applicable) in the diary.
- p At any time the diary is in a subject's possession, they will enter HAE attacks and relevant details and dosing information (as applicable) at least once per day.
- q On Day 14, a blood sample for plasma PK and plasma kallikrein analysis will be drawn prior to dosing ( $< 5$  min) and at 1, 2, 3, 4, 5, 6, 8, and 24 hours postdose (i.e., on Day 15); Day 29 will be trough samples. If the subject is unable to provide serial PK samples on Day 14, steady state PK samples may be obtained on Day 28, with a 24-hour PK sample drawn at the scheduled visit on Day 29. In this case, trough PK samples will be drawn on Day 14. If the subject has a Day 29 visit for the 24-hour PK sampling, concomitant medications and AEs should also be assessed at the visit. Within 6 hours postdose, an acceptable window around each PK draw is  $\pm 10$  minutes. After 6 hours, an acceptable window is  $\pm 20$  minutes. Plasma PK and plasma kallikrein samples will be collected prior to in clinic dosing on Day 1 and Day 14. The Day 29 samples will be collected approximately 24 hours post-last dose.
- r Cleaved HK and an additional sample for possible exploratory analysis used to elucidate PD properties of BCX7353 will be drawn.
- s Subjects will take their study drug in the clinic on Day 1, Day 14 and Day 15 (Day 28 if subjects must complete serial PK on the last dose). Subjects will take all other doses at home as instructed. The last day of study drug dosing is Day 28.

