**Table 4: Data Display Treatment Descriptors**

Study Part	Treatment Group	Treatment Description	Final Data Display
			Treatment Description
Parts 1, 2 and 3 Combined	Group 1	placebo QD orally for 28 days	Placebo
Part 1	Group 2	350 mg BCX7353 QD orally for 28 days	BCX 7353 350 mg
Part 2 and 3 Combined	Group 3	250 mg BCX7353 QD orally for 28 days	BCX7353 250 mg
	Group 4	125 mg BCX7353 QD orally for 28 days	BCX7353 125 mg
Part 3	Group 5	62.5 mg BCX7353 QD orally for 28 days	BCX7353 62.5 mg

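### SAP 13.2 gives the AUCtau interval as 8 hours for q8h dosing in a once-daily trial; programmed literally, this would make AUCtau about 2.4 to 2.9 times too low and CL/F too high by the same factor

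*SAP*

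**What the plan says.** The parameter table in SAP 13.2 describes AUCtau as the area across the dosing interval and attaches the gloss "ie, 8 hours for q8h dosing". Protocol Table 7 describes the same parameter with the gloss "i.e., 24 hours for once daily dosing".

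The rest of the SAP describes a once-daily trial. SAP Table 4 lists only once-daily groups, for example "350 mg BCX7353 QD orally for 28 days". The serial PK samples in SAP Table 1 run from predose through 8 hours to 24 hours.

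Other parameters in the same SAP table bear on the question:
- CL/F is "Apparent oral clearance after administration of the drug calculated as" dose over AUCtau.
- Cav,ss is "Average steady-state plasma drug concentration during multiple-dose administration", with no formula given.
- Ctau is "Observed drug concentration at the end of the dosing interval".

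Later in SAP 13.2, the trough concentrations are those "obtained pre-dose or 24 hour post-dose on Days 14, 15, 28 and 29 (as applicable").

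**The concern.** The gloss opens with ie, so it states the value of tau and does not merely offer an example. It is also the only number of hours that the SAP's parameter table gives for the interval. No arm is dosed every 8 hours, so the number contradicts both the SAP's own design and the protocol.

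A literal program would give no warning. The schedule includes an 8-hour sample, so an AUC from 0 to 8 hours would compute without missing values. SAP 9.1 wants outside statisticians to be able to replicate the analyses, and one who followed the parameter table to the letter would get a different AUCtau.

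AUCtau and CL/F are listed secondary endpoints (SAP 2.2.2). AUC enters the dose-proportionality models (SAP 13.2), and AUCtau enters the exposure-response analyses against attack rate (SAP 14.2).

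**Working it through.** **Inputs.** From Protocol 5.3.1 (healthy subjects): exposure increases 3.0- to 5.1-fold on repeated dosing; effective half-life is 41 to 75 h; Tmax is about 2 to 5 h in Western subjects and 2 to 6 h in Japanese subjects. At 250 mg once daily, geometric mean AUCtau is 3710 ng·h/mL with Cmax 217 ng/mL (Western), and 4180 ng·h/mL with Cmax 261 ng/mL (Japanese).

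**Step 1: which tau do the documents' own figures use?** Effective half-life = ln 2 × tau / ln[R/(R − 1)], where R is the accumulation ratio.
- tau = 24 h: R = 3.0 gives 16.64/0.4055 = 41.0 h; R = 5.1 gives 16.64/0.2183 = 76.2 h. This reproduces the stated 41 to 75 h to within 2%.
- tau = 8 h: the same ratios give 13.7 h and 25.4 h, which do not match.

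Second check: average concentration cannot exceed Cmax.
- 3710/24 = 155 is below 217, but 3710/8 = 464 is above it.
- 4180/24 = 174 is below 261, but 4180/8 = 523 is above it.

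The reported AUCtau values are possible with 24 h and impossible with 8 h.

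**Step 2: AUCtau if 8 h were applied.** The factor is AUC(0–24)/AUC(0–8) at steady state.
- Simple exponential decline: AUC(0–8)/AUC(0–24) = (1 − e^(−8k))/(1 − e^(−24k)). Half-life 41 h gives 0.379 (factor 2.64); 75 h gives 0.358 (factor 2.79).
- One-compartment oral model, half-life 41 to 75 h, Tmax 2 to 6 h: factor 2.68 to 2.92.
- Curve fitted to the reported AUCtau and Cmax at 250 mg (linear rise to Cmax at 2 or 5 h, exponential fall to trough): factor 2.37 to 2.62.
- Bounds: AUC(0–8) cannot exceed 8 × Cmax, so the factor is at least 3710/(8 × 217) = 2.1 (Western) and 4180/(8 × 261) = 2.0 (Japanese). A flat profile would give 3.0.

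Taken together, the factor is about 2.4 to 2.9.

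**Step 3: CL/F.** At 250 mg with tau = 24 h, 250 mg/3710 ng·h/mL = 67.4 L/h. The fitted Western curve gives AUC(0–8) of 1502 (Tmax 2 h) or 1415 ng·h/mL (Tmax 5 h), hence CL/F of 166 or 177 L/h.

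**Step 4: Cav,ss.** Assume the usual AUCtau/tau, which the SAP does not write out. The ratio of the 8-hour to the 24-hour average is three times the AUC fraction. The one-compartment calculations have AUC fractions down to 0.341, so 3 × 0.341 = 1.02; the simple exponential at 41 h gives 3 × 0.379 = 1.14. The fitted curve gives 1.14 to 1.26. The shift is about 2 to 26%.

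**Step 5: Ctau.** Ctau is an observed concentration and is not computed from AUC. Read at 8 h it would be too high by a factor of 1.14 to 1.31 (one-compartment model) or 1.7 to 2.1 (fitted curve). However, SAP 13.2 fixes troughs at predose or 24 h, so it should not be read there.

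**Step 6: comparisons between doses.** If AUC at every dose is divided by a common factor f, the power model ln AUC = a + b ln(dose) changes only in a, by −ln f. The slope b, the dose-normalised ratios to 125 mg and the correlation coefficients with attack rate are unchanged. This is approximate, because f is common only if profile shapes are similar across doses.

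**The case against.** The strongest reply is that the gloss is a leftover that nobody would execute. The operative words concern the dosing interval, which is 24 h in every group. The abbreviation list defines AUCtau without any 8 hours, and both the serial sampling and the troughs go to 24 h. The interim results in Protocol 5.3.3.2 put this study's AUCtau at 0.98, 0.86 and 1.15 times the healthy-subject values for 350, 125 and 250 mg, with no two- to three-fold drop.

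Most of this stands, and it makes the error conditional. It does not remove the contradiction. The documents do not say which SAP version produced the interim PK, so those ratios are supporting evidence and not proof. Silent correction cannot be taken for granted either: SAP 12.3 computes expected capsules at 3 per day, while Protocol 9.1 gives 2 per day in Part 3.

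A reader might also infer that Cav,ss and Ctau would be wrong by almost three-fold and that dose selection is compromised. The documents do not support this. The shorter divisor cancels most of the Cav,ss error, troughs are fixed at predose or 24 h, and a common factor largely cancels between doses.

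**Conclusion.** The 8-hour gloss is a definite error in the definition of a listed secondary endpoint, and it should be corrected. If applied literally, it would make AUCtau about 2.4 to 2.9 times too low and CL/F too high by that factor; Vz/F would follow if computed from CL/F. Comparison with the AUCtau values in Protocol 5.3.1 and 5.3.3.2 would then fail.

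It would be too strong to say that the PK results will be wrong. That requires someone to program the gloss against the rest of the SAP, and the reported figures fit 24 h.

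The size rests on assumed curve shapes. Protocol 5.3.1 describes a second peak and a biphasic decline, which none of these curves captures in full; the bounds of at least 2.0 to 2.1 from Cmax do not depend on shape. The documents do not say where the q8h wording came from.

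**What to change.** In SAP 13.2, replace the parenthesis in the AUCtau row with wording that sets tau to 24 hours for once-daily dosing, as in Protocol Table 7. It would also help to state in the Ctau row that Ctau is the 24-hour post-dose concentration, in line with the trough paragraph of the same section. Make the change before the PK analysis is programmed, and confirm that any PK program already in use integrates to 24 h. The cost is one line of SAP text; no data collection, sample size or efficacy analysis changes.

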In Western subjects (Parts 1 and 2) following single oral doses of BCX7353 up to 1000 mg and multiple oral doses of up to 500 mg QD administered under fasting conditions,  $C_{max}$  was reached approximately 2 to 5 hours after dosing. There was a prolonged absorption phase followed by a distribution/elimination phase. A second "peak" occurred around 5 hours after dosing, after the time of a meal. The double-hump PK profiles suggest that BCX7353 may undergo enterohepatic recirculation. BCX7353 plasma concentrations then declined biphasically. The effective half-life of BCX7353 was calculated to be 41 to 75 hours, based upon the 3.0- to 5.1-fold increase in exposure with 7 to 14 days of BCX7353 dosing. Across Part 2 cohorts, analysis of trough values indicated that steady-state conditions were achieved from 6 to 12 days post first dose.

In Part 1, examination of point estimates for dose-normalized  $C_{max}$  and  $AUC_{0-inf}$  indicated that both  $C_{max}$  and  $AUC_{0-inf}$  increased in a more than dose-proportional manner over the 30 mg to 1000 mg dose range; point estimates and associated 95% confidence interval (CI) ranges suggest reasonable dose-proportionality with doses between 250 mg and 500 mg for  $C_{max}$ . In Part 2 cohorts dosed for 7 days, there was a slightly greater than dose proportional increase in exposure

(AUCtau and Cmax) over the 125-mg to 500-mg dose range. With 4-fold increases in dose, there was a 5.1 and 5.3-fold increase in the geometric mean values for AUCtau and Cmax, respectively.

After a high-fat breakfast, there was no significant effect on AUC0-24; the geometric mean value (coefficient of variation [CV]%) for AUC0-24 was 995 (25) ng•hr/mL under fasting conditions compared with 944 (28) ng•hr/mL under fed conditions. Also, no effect was observed on the geometric mean Cmax values. Given that there was no appreciable difference in the PK with or without a high-fat meal, the recommendation in future clinical studies will be to administer BCX7353 with food. Administration with food may mitigate any potential for gastrointestinal AEs.

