BCX7353 concentration-time profile following single and multiple dose administration in Japanese subjects (Part 3) was similar to those observed in the Western subjects (Parts 1 and 2). Maximal plasma BCX7353 concentrations were achieved at approximately 2 to 6 hours postdose. The second peak observed during absorption occurs after the administration of a meal. BCX7353 plasma concentrations then declined bi-exponentially with a geometric mean terminal elimination half-life of 73 hours following repeated dosing at 250 mg QD. After repeated dosing, the geometric mean accumulation ratio in AUCtau was approximately 4-fold, which is consistent with the observed long half-lives. In comparison to Western subjects dosed 250 mg for 7 days, the plasma exposure appeared to be slightly higher in Japanese subjects who received the same oral administration of BCX7353 (geometric mean AUCtau of 4180 vs 3710 ng•hr/mL and geometric mean Cmax of 261 vs 217 ng/mL).

The effect of BCX7353 on the target enzyme, plasma kallikrein, was evaluated by comparing specific amidolytic activity in plasma samples taken after drug administration to baseline samples. A rapid and substantial inhibition of plasma kallikrein activity was observed following single 250 mg or higher doses of BCX7353. The response was generally dose dependent with a more sustained effect observed over the 24-hour period with the 500-mg and 1000-mg single doses.

Oral administration of multiple doses of BCX7353 at 125 mg QD for 7 days imparted measureable plasma kallikrein inhibition through a dosing interval, achieving mean maximal reductions of approximately 70% around the time of Tmax. Higher doses of BCX7353 (250 mg QD or higher) provided more potent inhibition that was more consistently sustained through a dosing interval, achieving approximately 90% inhibition across an interval on average. Similar levels of kallikrein inhibition were observed in Japanese subjects (Part 3) as compared to Western subjects (Parts 1 and 2) given comparable doses. Potent kallikrein inhibition of approximately 90% was consistently sustained throughout the dosing interval after administration of BCX7353 at 250 mg QD. The BCX7353 concentration and kallikrein inhibition relationship was well-described by a sigmoidal Emax model; drug effect on the target enzyme was highly correlated with exposure (r = 0.921 for Parts 1, 2, and 3 combined).

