#### **5.4.2. Rationale for Study Design**

This is a Phase 2a study designed to assess the safety, efficacy, and PK of BCX7353 for the prophylactic treatment of subjects with HAE over a 28-day treatment period.

A parallel group design was considered the most appropriate study design to evaluate BCX7353 relative to other doses of BCX7353 and relative to placebo because of its very long half-life. The terminal half-life of BCX7353 was estimated at approximately 60 hours at doses ranging from 100 mg to 1000 mg in the single ascending dose Part 1 of Study BCX7353-101. Given this long half-life it would be more difficult to minimize carry-over effects in a study utilizing a cross-over design.

Since Study BCX7353-203 is the initial proof-of-concept study of BCX7353 in adult subjects with HAE, enrollment of subjects known to the study investigators as having frequent HAE attacks allows evaluation of the BCX7353 treatment effect of the highest proposed clinical dose (350 mg) over a short period (28 days) relative to placebo. This will prudently establish proof-of-

concept and risk/benefit at the dose of BCX7353 modeled to provide the most complete plasma kallikrein suppression through a daily dosing interval, 350 mg QD. A tiered enrollment approach of analyzing data from the first 24 subjects completing either placebo or BCX7353 350 mg QD treatment prior to enrolling a maximum of 36 subjects will help to limit the number of subjects exposed to an investigational product that has undetermined efficacy. Additional BCX7353 doses down to 62.5 mg QD will be evaluated in subjects once the risk/benefit balance has been ascertained at this highest dose.

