#### **11.1.13. Pharmacokinetics**

All plasma samples for determination of BCX7353 concentrations will be analyzed using a validated liquid chromatography-mass spectroscopy assay. Instructions for collection, processing, storage, and shipment of PK samples will be provided to the clinical site in the laboratory manual. Samples may also be analyzed on an exploratory basis for possible BCX7353-metabolites.

On Day 14 serial blood samples will be drawn for PK analysis predose and at the following time points: 1, 2, 3, 4, 5, 6, 8, and 24 hours postdose. For the 24 hour postdose samples, subjects will return to the clinic and have the blood sample drawn prior to dosing on Day 15. On Day 29, a trough PK blood sample will be drawn.

However, if the subject is unable to provide serial PK samples on Day 14, only the predose sample (i.e., trough PK sample) will be obtained on Day 14 and steady state serial PK samples will be obtained on Day 28, with a 24-hour PK sample drawn at the scheduled visit on Day 29.

Within 6 hours postdose, an acceptable window around each PK draw is  $\pm 10$  minutes. After 6 hours, an acceptable window is  $\pm 20$  minutes. Predose samples should be drawn within 5 minutes of the next scheduled dosing time.

Plasma BCX7353 PK parameters will be calculated as applicable, including the following: maximum concentration ( $C_{max}$ ), time to  $C_{max}$  ( $T_{max}$ ), area under the concentration versus time curve (AUC), and 24 hour half-life ( $t_{1/2}$ ) in plasma.

Actual date and time of PK sample collection will be recorded in the eCRF. In addition, the site should verify that the time of last dose taken at home prior to the visit is documented in the diary.

The lab performing bioanalytical analysis will be provided the randomization scheme. Two samples will ordinarily be analyzed for subjects randomized to placebo: the 4 hour postdose sample on Day 14 and the trough at Day 29.

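### Terminal half-life, lambda-z and Vz/F are planned from a 24-hour steady-state profile that cannot identify a terminal phase of about 60 to 73 hours

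*SAP*

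**What the plan says.** **Parameters.** SAP 2.2.2 puts half-life, lambda and apparent volume among the secondary endpoints, as steady-state PK parameters. Protocol 13.2.6, Table 7 defines t1/2 as "Estimate of the terminal elimination half-life of the drug", and the SAP 13.2 table does likewise. Protocol 11.1.13 instead describes a 24-hour half-life.

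**Sampling.** Protocol 11.1.13 takes serial samples on Day 14 (Day 28 if Day 14 is not possible), before the dose and "at the following time points: 1, 2, 3, 4, 5, 6, 8, and 24 hours postdose". Afterwards, "On Day 29, a trough PK blood sample will be drawn". The schedule (Protocol Table 3) has no PK sample at Day 44, and Day 1 has only a predose sample.

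**What is known of the drug.** Protocol 5.4.2: "terminal half-life of BCX7353 was estimated at approximately 60 hours", after single doses in healthy subjects. Protocol 5.3.1 reports a "geometric mean terminal elimination half-life of 73 hours following repeated dosing at 250 mg QD" in healthy Japanese subjects, a second peak around 5 hours, and for Western subjects: "BCX7353 plasma concentrations then declined biphasically".

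**Acceptance rule.** SAP 13.2 uses noncompartmental analysis over the sampling interval and in general requires "a minimum of three time points in the terminal phase with unadjusted" R-squared of at least 0.7. It adds that estimation depends on characterising the terminal phase accurately, judged from individual profiles, and that values the sponsor's clinical pharmacologist considers unreliable may be left out of the summaries.

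**The concern.** A terminal slope can be read only where the terminal phase dominates and the concentration falls enough to measure. Here the whole window is 24/60 = 0.40 to 24/73 = 0.33 of one half-life. If the 5-hour second peak carries over, the post-peak points are 6, 8 and 24 hours, exactly the SAP minimum of three.

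Any remaining distribution phase steepens the fitted line. That raises lambda-z and lowers t1/2 (ln 2 / lambda-z) and Vz/F (CL/F divided by lambda-z) by the same factor.

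Describing PK in HAE subjects is a secondary objective. A value labelled terminal and well below 60 hours, set beside the healthy-subject figures, would invite the reading that HAE patients eliminate the drug faster.

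**Working it through.** **1. Reproduce the protocol's effective half-life.** Protocol 5.3.1: "The effective half-life of BCX7353 was calculated to be 41 to 75 hours, based upon the 3.0- to 5.1-fold increase in exposure". With 24-hour dosing, t1/2,eff = 24 × ln 2 / ln[R/(R − 1)].
- R = 3.0: 16.64 / 0.4055 = 41.0 h.
- R = 5.1: 76.2 h (R = 5.05 gives 75.4 h).

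The stated range reproduces within rounding, so the long half-life is internally consistent.

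**2. Fall available in the last interval.** From 8 to 24 h the fall is 1 − 2^(−16/t1/2): 16.9% at 60 h and 14.1% at 73 h. The interval is 16/60 = 0.27 or 16/73 = 0.22 of a half-life.

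**3. Two-point check from the 250 mg figures.** Inputs: Cmax 217 ng/mL, healthy subjects (Protocol 5.3.1); the same scaled by the HAE/healthy AUC ratio of 1.15 (Protocol 5.3.3.2), 249.6; mean HAE trough 132 ng/mL (Protocol Table 2). Apparent t1/2 = Δt × ln 2 / ln(Cmax/trough).
- Δt = 20 h: 13.86 / ln(217/132) = 27.9 h; 13.86 / ln(249.6/132) = 21.8 h.
- Peak anywhere from 2 to 5 h (Δt 22 to 19 h): 30.7 down to 20.7 h.

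Against 60 to 73 h that is 60/30.7 = 2.0 to 73/20.7 = 3.5 times too short.

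**4. Modelled profiles.** Steady state with first-order absorption and biexponential disposition, terminal half-life fixed, error-free log-linear fits to 6/8/24, 5/6/8/24 and 4/5/6/8/24 h. The first profile uses the 250 mg figures: Cmax/Cavg = 217/(3710/24) = 1.40, and Ctau/Cavg = 132/(3710 × 1.15/24) = 0.74. The flatter two are assumptions; the fit met the last only approximately.

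| Cmax/Cavg, Ctau/Cavg | True 60 h: fitted (true/fitted) | True 73 h: fitted (true/fitted) |
|---|---|---|
| 1.40, 0.74 | 22.5–23.8 h (2.5–2.7) | 22.4–23.6 h (3.1–3.3) |
| 1.30, 0.80 | 29.2–31.0 h (1.9–2.1) | 29.8–31.8 h (2.3–2.5) |
| 1.25, 0.85 | 46.8–51.8 h (1.2–1.3) | 36.7–39.5 h (1.9–2.0) |

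**5. Does the R-squared rule catch this?** For the first profile with an assumed 10% error, 97% of simulated 6/8/24 h fits pass, with a median near 24 h; at most 0.4% reach the true value. Separate error-free fits at 6, 8 and 24 h, with an assumed distribution half-life of 3 to 8 h and a true 60 h, gave 23 to 34 h with R-squared 0.98 to 1.00. The wrong slope fits well.

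**6. No distribution phase at all (6/8/24 h, true 60 h; error levels assumed).**

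| Error CV | Pass rule | Median of passing | 5th–95th percentile |
|---|---|---|---|
| 5% | 92% | 59 h | 40–110 h |
| 10% | 63% | 49 h | 28–130 h |
| 15% | 47% | 39 h | 21–120 h |

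At a true 73 h the medians are 70, 54 and 42 h.

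**7. Effect on Vz/F, 250 mg in HAE.** AUCtau = 3710 × 1.15 = 4267 ng·h/mL, so CL/F = 250 mg / 4267 ng·h/mL = 58.6 L/h. Vz/F = 58.6 × t1/2 / 0.693: about 5070 to 6170 L at 60 to 73 h, against about 2000 to 2700 L at 24 to 32 h.

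**The case against.** **The SAP has a safeguard.** It makes estimation conditional on an accurate terminal phase, allows unreliable values to be excluded, and lists the parameters only as ones that may be estimated. This stands, so it cannot be said that biased values will be reported. But exclusion is discretionary and has no span criterion, and with no sample between 8 and 24 h, inspection cannot show where distribution ends.

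**The protocol already speaks of a 24-hour half-life.** True in Protocol 11.1.13, but Table 7 and SAP 13.2 say terminal, so the texts conflict.

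**The bias is not a document figure.** This stands. No HAE Cmax or HAE terminal half-life is given. Step 3 pairs a healthy-subject, Day 7 geometric mean with an HAE arithmetic mean. The 5-hour second peak was seen under fasting dosing, whereas this study doses with food, and no distribution half-life is stated.

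**A reader might infer that the estimates are mere noise, or that the rule keeps only profiles that look steep by chance.** Neither follows. At 5% error without a distribution phase the median is close to the truth, and at 10% about 32% of passing profiles exceed 60 h. No error level is documented.

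**A reader might infer that washout or carry-over planning depends on this estimate.** Nothing in the documents says so. The parallel design rests on the earlier healthy-subject half-life (Protocol 5.4.2). The HAE-versus-healthy comparison uses AUCtau (Protocol 5.3.3.2). Dose proportionality uses AUC and Cmax (SAP 13.2), and the named exposure-response analyses use concentrations, Cmax, AUCtau and Ctau (SAP 14.2).

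**Conclusion.** The point holds as a mismatch between label and sampling. A 24-hour profile cannot identify a terminal phase of about 60 to 73 hours. Half-life and Vz/F would tend to be too low and lambda-z too high, by roughly 1.2- to 3.5-fold depending on the profile. Without a distribution phase the problem is imprecision, whose size depends on the assumed error. The rule of three points and R-squared of at least 0.7 does not screen out either.

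A reader might settle on a fixed two-fold bias. The documents do not support one figure: the range rests on assumed profiles, mixed healthy and HAE data, and healthy-subject half-lives taken to apply in HAE.

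The reach is limited to three descriptive parameters. The primary efficacy analysis, AUCtau, Cmax, Ctau, Cav,ss and CL/F are unaffected. The correction is still worth making, because these parameters are listed secondary endpoints and the change is nearly free.

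**What to change.** In Protocol Table 7 and SAP 2.2.2 and 13.2, do one of the following:

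- Delete t1/2, lambda-z and Vz/F.
- Relabel them as apparent within-interval (0-24 h) values, not terminal and not to be compared with the healthy-subject terminal half-life, and align Protocol 11.1.13 with that label.
- Report lambda-z and derived values only when the fitted window meets a stated minimum span in half-lives. Measure the span against the 60 to 73 h prior: 6 to 24 h is then 18/60 = 0.30 or 18/73 = 0.25 of a half-life. Measured against each subject's own estimate, the rule would favour the steepest, most biased fits.

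The cost is wording only. The downside is that no terminal half-life is reported for HAE subjects. An accumulation-based effective half-life is not available either, because Day 1 has only a predose sample.

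A Day 44 PK tube could be considered but is unproven. At 60 h the 125 mg trough of 42.8 ng/mL would be about 42.8 × 2^(−360/60) = 0.7 ng/mL on Day 44, and lower later in the +7-day window. The assay limit is not stated, and two points (Days 29 and 44) would not meet the SAP's three-point rule.
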